## 12.0 REPORTING OF ADVERSE REACTIONS

### ADVERSE EVENT DEFINITIONS

Adverse event means any untoward medical occurrence associated with the use of the drug in humans, whether or not considered drug related.

Adverse reaction means any adverse event caused by a drug.

Suspected adverse reaction means any adverse event for which there is a reasonable possibility (definitely or probably) that the drug caused the adverse event. Suspected adverse reaction implies a lesser degree of certainty about causality than “adverse reaction”

Serious Adverse Event: Any untoward medical occurrence associated with the use of a drug in humans, whether or not considered drug related. Specifically, results in death, is life-threatening, requires inpatient hospitalization or causes prolongation of existing hospitalization, results in persistent or significant disability/incapacity, is a congenital anomaly/birth defect, or is an important medical event (defined as a medical event(s) that may not be immediately life-threatening or result in death or hospitalization but, based upon appropriate medical and scientific judgment, may jeopardize the subject or may require intervention [e.g., medical, surgical] to prevent one of the other serious outcomes listed in the definition above.) Also, included: any subject death within 30 days of the last dose of study drug, regardless of the causality.

Scheduled protocol inpatient hospitalizations do not meet the criteria above for recording and reporting as an SAE. Only events which would prolong the scheduled inpatient stay to be resolved or unplanned hospitalizations due to events occurring between scheduled inpatient stays should be recorded as SAEs.

Life-threatening, suspected adverse reaction. A suspected adverse reaction is considered “life-threatening” if, in the view of either the Investigator (i.e., the study site principal investigator), its occurrence places the patient or research subject at immediate risk of death. It does not include a suspected adverse reaction that had it occurred in a more severe form, might have caused death.

Unexpected, suspected adverse reaction. A suspected adverse reaction is considered “unexpected” if it is not listed in the general investigational plan or clinical protocol; or is not listed at the specificity or severity that has been previously observed and/or specified.

All observed or volunteered adverse events (serious or non-serious) and abnormal test findings, regardless of study group or suspected causal relationship to the study drug(s) will be recorded in the subjects’ case histories. For all adverse events, sufficient information will be pursued and/or obtained so as to permit 1) an adequate determination of the outcome of the event (i.e., whether the event should be classified as a *serious adverse event*) and; 2) an assessment of the casual relationship between the adverse event and the study drug(s).

Adverse events or abnormal test findings felt to be associated with the study drug(s) will be followed until the event (or its sequelae) or the abnormal test finding resolves or stabilizes at a level acceptable to the Principal Investigator.

In the event of an adverse event the first concern will be for the safety of the subject.

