### **2.18 Early experience with the regimen.**

The first five patients were treated with 600mg of Hydroxychloroquine with one patient deemed a complete response. Out of the 13 patients treated with combination HCQ/IL-2 therapy using 1200 mg of Hydroxychloroquine, two patients experienced pronounced hypotension and tachycardia. Furthermore, one patient died from pulmonary emboli, not attributed to therapy. The cardiac events are consistent with IL-2 toxicities, but were observed somewhat earlier in the course of treatment. For that reason we are accruing another 21 patients to assess response in addition to the first five patients at the lower 600mg/d dose.

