## 9.0 EVALUATION AND MANAGEMENT OF TOXICITY (DOSE MODIFICATION)

### 9.1 General

Investigator/Sub-investigators, regulatory, CRS management, clinical research coordinators, clinical research associates, data managers, and clinic staff meet regularly in disease center Data Safety Monitoring Boards (DSMB) to review and discuss study data to include, but not limited to, the following:

- serious adverse events
- subject safety issues
- recruitment issues
- accrual
- protocol deviations
- unanticipated problems
- breaches of confidentiality

All toxicities encountered during the study will be evaluated on an ongoing basis according to the NCI Common Toxicity Criteria version 4.0 and recorded prior to each course of the investigational therapy. Any modifications necessary to ensure subject safety and decisions to continue, or close the trial to accrual are also discussed during these meetings. All study data reviewed and discussed during these meetings will be kept confidential. These reviews are summarized by each respective disease center and submitted to the University of Pittsburgh Cancer Institute's Data and Safety Monitoring Committee (UPCI DSMC) for their monthly review of all disease centers' studies. The UPCI DSMC will provide oversight for this study. At the time of renewal a summary of all serious adverse events and modifications will also be reported to the UPCI DSMC.

Any modifications necessary to ensure patient safety will be submitted to the IRB prior to implementation. The IRB will be notified of any change in the risk/benefit ratio which would affect whether the study should continue. All protocol deviations or breaches of confidentiality will be reported to the IRB according to IRB guidelines. If any literature becomes available which suggests that conducting this trial is no longer ethical the study will be terminated and the IRB will be notified of the new findings in the form of an Unanticipated Problem submission. All study treatment associated adverse events that are serious, at least possibly related and unexpected will be reported to the IRB. DSMC reports and approval will be submitted to the IRB at the time of renewal.

All records related to this research study will be stored in a locked environment. Only the researchers affiliated with the research study and their staff will have access to the research records.

Safety data for each patient at the end of each cycle of IL-2 will be provided by all sites to the PI at UPCI.

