**9.3.3 Management of Arrhythmias/Myocarditis.** If significant arrhythmias occur at any stage in the patient's treatment (whether on pressor agents or not), the possibility of myocardial ischemia/infarction must be excluded by both EKG and cardiac enzyme assessment. Patients who develop atrial fibrillation should have IL-2 doses held. Therapy may resume when the patient converts to normal sinus rhythm and is hemodynamically stable. If a significant supraventricular arrhythmia occurs while a patient is on dopamine therapy; neosynepherine should also be substituted for dopamine as initial blood pressure

support. Patients experiencing sustained ventricular tachycardia or documented myocardial ischemic episodes during therapy should not receive further treatment with IL-2. Patients with myocarditis may resume treatment in subsequent courses if CPK returns to normal. A cardiac ECHO documenting normal cardiac function should be performed prior to restarting therapy.

**9.3.4 Management of Neurotoxicity.** Doses are held rather than reduced for neurotoxicity. If Grade 4 neuro-cortical toxicity is encountered and is not reversible within 48 hours, no further treatment should be given and the patient should be removed from the study. If Grade 4 toxicity is reversible to Grade 1 within 48 hours, future treatment may be considered (in subsequent courses) if the patients shows any evidence of tumor regression and as discussed with the patient.

**9.3.5 Metabolic Acidosis.** In the course of IL-2 therapy, when a patient's  $\text{HCO}_3$  falls to below 20,  $\text{NaHCO}_3$  should be added to the maintenance IV infusion. Should the  $\text{HCO}_3$  level fall below 18, IL-2 therapy should be held, and bolus infusions of  $\text{NaHCO}_3$  should be instituted. IL-2 therapy may resume if repeat  $\text{HCO}_3 > 18$ . Sodium acetate may be substituted for  $\text{NaHCO}_3$  per institutional policy.

**9.3.6 Low Urine Output.** Fluid boluses and 'renal' dose dopamine may be administered. Weight gains/edema may serve as a basis for holding doses.

**9.3.7 Other Toxicities.** Increases in the serum creatinine to 2.0-3.5 mg/dl and total bilirubin to 3.0-10.0 mg/dl are common and reversible upon cessation of treatment. Doses of IL-2 have not generally been withheld for renal and hepatic dysfunction alone. Although toxicity may become severe, recovery usually occurs following cessation of IL-2 and vigorous supportive care is warranted.

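### Section 12 gives two conflicting SAE rules for scheduled IL-2 stays, so sites may classify the same non-fatal life-threatening event differently

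*Combined protocol and SAP*

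**What the plan says.** The SAE definition in Section 12.0 (Adverse Event Definitions) lists alternatives, any one of which is enough: "Specifically, results in death, is life-threatening, requires inpatient hospitalization or causes prolongation of existing hospitalization", then disability, congenital anomaly and important medical events. It closes with a separate clause on deaths: "Also, included: any subject death within 30 days of the last dose of study drug, regardless of the causality".

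The next paragraph deals with planned admissions. Its first sentence is "Scheduled protocol inpatient hospitalizations do not meet the criteria above for recording and reporting as an SAE". Its second sentence starts "Only events which would prolong the scheduled inpatient stay to be resolved or unplanned hospitalizations due to events occurring between scheduled inpatient stays" and ends by saying that these are what should be recorded as SAEs. It carries no qualifier such as 'for the hospitalization criterion'.

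Further on, under Reporting of Suspected Adverse Reactions, Section 12 requires every event that meets the SAE definition to go on a MedWatch 3500A form to the research coordinators and the IL-2 manufacturer. That instruction has no restriction tied to the length of stay.

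**The concern.** The first sentence on scheduled admissions already does what is needed: a planned IL-2 admission is not an SAE merely because the patient is in hospital. The second sentence goes further. Taken at its word, it replaces the whole list of criteria with one test, namely whether the event lengthened the stay or caused an unplanned admission between stays. An event can be life-threatening and still pass without doing either.

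This matters because IL-2 is given in these stays, so the sentence applies when acute toxicity of the combination is most likely. Section 2.17 says the combination has not been used in earlier trials. Section 2.18 reports that, among 13 patients at 1200 mg/d of hydroxychloroquine (HCQ), "two patients experienced pronounced hypotension and tachycardia", somewhat earlier in treatment than expected. That is the kind of acute inpatient event whose SAE status could turn on which sentence a site follows. In a multi-center trial, two sites could classify the same event differently and both be following the protocol.

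**Working it through.** No stated figure needs reproducing, so the check sets the rules side by side on four cases.

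| Case | Definition and MedWatch instruction | 'Only' sentence, read literally |
|---|---|---|
| (a) Life-threatening, disabling or important medical event in a planned stay, resolved without prolonging it | SAE | Not an SAE |
| (b) Death during a planned stay | SAE: death criterion, and the 30-day clause | Not within its words, but the 30-day clause expressly includes it |
| (c) Event that prolongs the stay, or an unplanned admission between stays | SAE | SAE |
| (d) The planned admission itself | Not an SAE | Not an SAE |

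The rules agree on (c) and (d). On (b) the express death clause largely settles the matter. On (a) they give opposite answers.

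**Can case (a) occur?** Section 9.4 equates Grade 4 with life-threatening. Section 9.3.4 provides for Grade 4 neuro-cortical toxicity that returns to Grade 1 within 48 hours. Section 6.2 schedules dosing on days 1 to 5 (or 6) and 15 to 19 (or 20). An event starting on day 2 and reversing within 48 hours is over by day 4 (2 + 2), inside a stay that runs to day 5 or 6. The protocol therefore provides for such an event. It does not say how often it happens.

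**How much of the trial is exposed?** From the Summary and Section 6.2:
- Planned stays: 2 per course × up to 3 courses = 6 at most.
- Inpatient days: 6 × 5 = 30 to 6 × 6 = 36 at most.
- IL-2 doses: 14 × 2 = 28 per course at most.

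These are ceilings. Later courses depend on how the tumor responds, so a patient who has one course has 2 stays, or 10 to 12 days. They measure exposure to the conflicting rule, not missed SAEs.

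**Which reports depend on the SAE label?**
- MedWatch 3500A forms to the coordinators and manufacturer (Section 12).
- IRB reports of serious, at least possibly related and unexpected events (Section 9.1).
- SAE review by the disease-center DSMB (Section 9.1).
- At renewal, "a summary of all serious adverse events and modifications will also be reported to the UPCI DSMC" (Section 9.1).

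**Which do not?**
- Recording of all AEs in case histories (Section 12).
- Daily AE assessment during IL-2, monthly toxicity scoring, and AE data pooled for monthly Multi-Center DSMC monitoring (Section 6.4.1).
- Severe adverse events sent at once to the coordinating center (Section 8.0).
- Previously unknown or severe toxicities reported to the FDA, with a copy to the manufacturer (Section 9.1).
- De-escalation of HCQ on treatment-limiting toxicities (Section 13.3.1), and the tabulation of IL-2 doses, maximal grade and treatment-limiting toxicities (Section 13.2.3).

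**The case against.** The best defense is that the sentence clarifies the hospitalization criterion and nothing else. It follows a sentence about scheduled hospitalizations, and both of its limbs mirror that criterion. The MedWatch instruction comes later and covers every event meeting the definition. This reading is possible, and it may be what the authors meant. But the planned admission is already exempted and prolongation is already in the definition, so on this reading 'Only' adds nothing. Nor does the MedWatch instruction settle the question: it refers back to the definition, and the sentence stands in the same definitions section. What survives of the defense is that this is a conflict of instructions, not a settled rule.

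Three stronger conclusions are tempting, and the documents do not support them.

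- A reader might infer that life-threatening and fatal events simply disappear from safety recording. They do not. Deaths within 30 days of the last dose are expressly SAEs whatever the cause, all AEs are recorded, and severe toxicities reach the coordinating center, the DSMC and the FDA by other routes. Those routes turn on severity, which is not seriousness, so they limit the harm without correcting SAE counts.
- A reader might take the line in Section 9.3.7, "Although toxicity may become severe, recovery usually occurs following cessation of IL-2", to show that recovery within the stay is the normal course. That line follows a discussion of creatinine and bilirubin rises and gives no recovery time. Section 9.2.4 warns that mental status changes can worsen after IL-2 is stopped.
- A reader might treat 2/13 = 15% as a rate of missed SAEs. Section 2.18 does not say whether those events were life-threatening, resolved within the stay, or were recorded as SAEs. They arose at 1200 mg/d, not the current 600 mg/d, and they were noticed and acted on. They illustrate the type of event only.

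It is also fair to say that no stopping rule or planned analysis uses SAE counts. The treatment-limiting toxicity route is not a clean safeguard, however: Section 13.1 takes its definition from Section 9.2, while Section 13.2.3 points to Section 10.5, which is about duration of response.

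**Conclusion.** The sentence is wrong as written. It conflicts with the SAE definition just above it and with the later MedWatch instruction, and the passages must be reconciled. The conflict bites on non-fatal life-threatening, disabling or medically important events that resolve within a scheduled IL-2 stay. For those events a site following the sentence literally would record no SAE, while a site following the definition would.

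The consequence is inconsistent or undercounted SAEs in the seriousness-dependent streams: MedWatch, IRB, DSMB and the DSMC renewal summary. Expected toxicities are the most exposed, because the Section 12 notification route for unexpected reactions would not pick them up. The number affected cannot be estimated from the documents, and no missed event is shown.

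This rests on two assumptions: that IL-2 is given during the scheduled stays, as Sections 6.2 and 12 indicate, and that at least some sites would apply the sentence as it reads. If every site took it as a gloss on the hospitalization criterion alone, nothing would be lost, but the text does not tell them to.

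**What to change.** Replace the 'Only' sentence with: *The scheduled admission for IL-2 is not itself an SAE. Any event during a scheduled stay that meets any SAE criterion above, including prolongation of the stay, and any unplanned hospitalization, is recorded and reported as an SAE.* This keeps the intended exemption for planned admissions and brings the paragraph into line with the definition and the MedWatch instruction.

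Ask sites to re-check inpatient Grade 4 events already recorded against this wording, so that SAE counts before and after the change are comparable.

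The cost is one sentence in an amendment and a look-back over AE data already held. The downside is more SAE forms for expected IL-2 toxicity.

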## REPORTING OF SUSPECTED ADVERSE REACTIONS

In the event of any unexpected or serious suspected adverse reaction, the PI, the institutional review board (per institutional reporting requirements), and Prometheus Drug Safety Department will be notified using the FDA Form 3500 MedWatch report. We will report all secondary malignancies occurring or following treatment by this protocol.

All events meeting the definition of a serious adverse event should be recorded on a MedWatch 3500A Form:

(<http://www.fda.gov/downloads/AboutFDA/ReportsManualsForms/Forms/UCM048334.pdf>)

and submitted to the Clinical Research Coordinators and Prometheus Laboratories' Drug Safety Department:

[name]  
[contact]  
Email: [[contact]](mailto:[contact])  
[contact]

[name]  
[contact]  
Email: [[contact]](mailto:[contact])  
[contact]

Prometheus Laboratories' Drug Safety Department  
Email: [[contact]](mailto:[contact])  
[contact].

In addition to completing appropriate patient demographic and suspect medication information, the report should include the following information within the Event Description (section 5) of the MedWatch 3500 form:

Reporting of toxicity will include:

- 1) Treatment regimen (dosing frequency, combination therapy)
  - 2) Protocol description (and number, if assigned)
  - 3) Description of event, severity, treatment, and outcome, if known
  - 4) Supportive laboratory results and diagnostics
  - 5) CTCAE Version 4.0 Term and Grade of event
  - 6) Investigator's assessment of the relationship (causality) of the adverse event to each investigational product and suspect medication
- the likelihood of the relationship between the toxicity and treatment (i.e., unrelated, unlikely, possibly, probably, or definitely related to treatment)
    - list alternate causality if event is unrelated or unlikely related to treatment (e.g. attributed to underlying disease, history of COPD, etc.)
  - whether the side effect noted falls within the expected toxicity profile of the agent employed

Follow-up information:

Additional information may be added to a previously submitted report by any of the following methods:

- Adding to the original MedWatch 3500 report and submitting it as follow-up
- Adding supplemental summary information and submitting it as follow-up with the original MedWatch 3500 form
- Summarizing new information and faxing it with a cover letter including subject identifiers (i.e. D.O.B. initial, subject number), protocol description and number, if assigned, suspect drug, brief adverse event description, and notation that additional or follow-up information is being submitted (The subject identifiers are important so that the new information is added to the correct initial report)

Occasionally Prometheus may contact the reporter for additional information, clarification, or current status of the subject for whom and adverse event was reported.

Assessing Causality:

Investigators are required to assess how likely it is that hydroxychloroquine caused or contributed to an adverse event (definitely, probably, possibly, or unlikely). The following factors should be considered when assessing relatedness.

- The temporal relationship of the clinical event to hydroxychloroquine administration
- The likelihood that IL-2 provides a sufficient explanation for the observed event.
- Other drugs, therapeutic interventions or underlying conditions that may provide a sufficient explanation for the observed event.

## 13.0 STATISTICAL ANALYSIS AND STUDY SIZE

### 13.1 Objectives and Design

The primary objective of this Phase II trial is to estimate the proportions of patients with metastatic RCC treated with high-dose IL-2 combined with hydroxychloroquine experiencing complete response, or any response. The secondary objectives are to compare response, time to progression and survival to historical data to determine the toxicity of the treatment regimen, to evaluate PD, and to examine correlative science endpoints. Disease endpoints are defined in Section 10.

The accrual goal is 39 participants. All study participants will receive the same high-dose IL-2 treatment, which is considered standard of care. The initial dose of HCQ will be 600 mg/day for all patients. If no limitations on additional dosing (treatment-limiting toxicities [TLTs], as defined in Section 9.2), dosing will continue at 600mg/d, otherwise, HCQ will de-escalate to 400 mg/d. Toxicity and response will be monitored after every three patients (Section 13.4), and will be stopped if the probability that treatment with IL-2+HCQ is excessively toxic or ineffective. The study may be opened more broadly to additional Cytokine Working Group sites whenever sufficient evidence has accrued that treatment with IL-2+HCQ is no more toxic or less effective than treatment with IL-2 alone.

### 13.2 Analysis Plan

The data will be analyzed for response, overall survival and other endpoints, as described in this section; data will only be analyzed as specified in Section 14.3.1 to ensure the toxicity of IL-2+HCQ is not unexpectedly high. All analyses will be performed using the most recent versions of SAS and/or R available.

- 13.2.1.** *Estimate the proportion of patients with metastatic RCC treated with IL-2 combined with hydroxychloroquine at 600mg/d who experience a clinical complete response.* Response is defined in Section 10.3. The probability of each category of response will be estimated. Secondary analyses will employ cumulative logit regression for increasing levels of response, with adjustment for demographic and clinical covariates. All point estimates will be accompanied by appropriate 95% confidence intervals.
- 13.2.2.** *Compare the response, overall survival and time to progression of patients with metastatic RCC treated with IL-2 combined with hydroxychloroquine to the published response of patients treated with high dose IL-2 alone.* Logistic and proportional hazards (Cox) regression will be used to compare clinical response, and OS and PFS, respectively, to examine the effect of HCQ on the efficacy of IL-2. Formal tests of non-inferiority are beyond the scope of this Phase II study, and these secondary analyses are not statistically powered.
- 13.2.3.** *Characterize the toxicity of IL-2 combined with hydroxychloroquine in patients with metastatic RCC: number of doses of IL-2 administered during the first course of therapy; toxicity after the scheduled 9th dose of IL-2; frequency of grade III and IV or unexpected or rare toxicities.* Number of doses, maximal toxicity grade and incidence of treatment-limiting toxicities (TLTs, as defined in Section 10.5) will be tabulated.

**13.2.4** *Evaluate the utility of known prognostic criteria for RCC patients on clinical outcome.* Prognosis is evaluated by whether the patient has 0, 1, or 2, or 3 or more of the following risk factors:

- lactate dehydrogenase (> 1.5 upper limit of normal)
- hemoglobin (< lower limit of normal)
- corrected calcium (>10mg/dL)
- Karnofsky performance status (< 80%)
- time from initial RCC diagnosis to start of interferon- $\alpha$  therapy of less than one year

This prognostic classification will be added to the baseline models described in Sections 13.2.1 to 13.2.3 to determine if any of the factors would significantly change the prognostic evaluation, and to the dynamic and post-treatment factors to potentially increase the statistical power.

**13.2.5** *Correlate baseline laboratory parameters (miRNAs pre- and post-IL-2; KIR genotyping; NK enumeration in the peripheral blood; DC function, TCR- $\zeta$  chain expression, arginase or arginine levels, proposed pathological/molecular prognosis classification described in Section 2.6) with toxicity, response, and survival.* Stepwise proportional hazards or logistic regression will be used to add variables to the models resulting from the analyses in Section 13.2.4.

**13.2.6** *Assess if changes in biomarkers measured in PBMC (Section 7.4) are associated with clinical response, overall survival or progression-free survival.* Stepwise proportional hazards or logistic regression will be used to determine if changes of any of the markers in Section 7.4 are related to patient outcomes, after adjusting for the prognostic criteria in 13.2.4.

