Follow-up data on these patients has now been accumulated through June 2010, with a median follow-up of over 10 years. Although some late relapses are still being observed, the response duration curve appears to have leveled off after the 30 month time point and 60% of complete responders remain in remission. In addition, 4 PRs who underwent surgical resection of residual disease while still in response remain alive and disease-free at a minimum of 65+ months. Therefore, many CRs remaining free from progression for more than thirty months and those PRs resected to NED after a response to high-dose IL-2 are unlikely to progress and may actually be cured. Thus, although the response rate to high-dose bolus IL-2 is modest, it can produce meaningful benefit in a small proportion of patients. Means to enhance this response are clearly in order.

The High Dose Aldesleukin "Select" trial was conducted to prospectively assess the ability of histologic, immunohistochemical and other pathologic tumor features to predict overall response rate and other outcomes (McDermott et al. 2011). This study enrolled 123 patients between November 2006 and July 2009, at many of the same Cytokine Working Group Institutions participating in the present study. Patients received high dose aldesleukin at a standard dose and schedule, and with standard recommendations for treatment modification for toxicity (Schwartzentruber 2001). The High Dose Aldesleukin "Select" study therefore represents a contemporaneous population of patients with similar baseline characteristics and aldesleukin treatment with which to compare to the current study with regard to outcomes and toxicity."

In that trial, overall response rate was 25% by independent review (95% CI 17.5-33.7) and 28% by investigator review (as to be performed in this study) (95% CI 20.5-37.3%). The distribution of MSKCC 2002 risk was 19/70/11% (Good/Int/Poor). Median PFS was 4.3 months (95% CI 2.5-4.7 mo) (comparable to prior studies where about half the patients progressed on the first scan). As seen previously, there was a "tail" of durable progression-free survival (PFS rate at 3 years was 11%). Median overall survival was 42.8 months (95% CI 35.6-51.9 months). Median duration of response was 20.6 months (CI 6.9-42.7 mo)

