### **13.3 Monitoring for Toxicity and Response**

**13.3.1** 21 additional patients will be enrolled at IL-2+HCQ 600 mg/day on this revised protocol. If one or more TLTs are observed, treatment will be de-escalated to IL-2+HCQ 400 mg/day.

**13.3.2** The number of overall partial and complete responses (**Table 8**) will be compared to the stopping rule described in Table 10 by the UPCI Multi-Center DSMC after every three patients become evaluable for response. For each number of evaluable patients in the left-hand columns, if the number of complete responses is less than or equal to the number in the right-hand column, the trial will be halted for lack of efficacy. The trial is derived from a Bayesian beta-binomial model with the prior determined by the number of complete responses observed in the high-dose arm of the randomized trial described in Section 2.3 (8/95). The values correspond to P (partial and complete response rate < 0.10) > 0.8.

# Patients	#Responses
18	0
21	1
24	1
27	1
30	2
33	2
36	2

*Table 8.* Monitoring rule for complete response. For the given number of patients in Column 1, if the number of partial or complete responses is less than or equal to the number in Column 2, the trial is halted for lack of efficacy.

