### 13.4 Justification of Design

The primary objective of this study is to estimate the clinical response rate of patients with metastatic RCC treated with IL-2 combined with hydroxychloroquine at 600mg/d. Assuming no TLTs occur and the trial is not closed early for toxicity or inadequate response (Section 13.3.2), there will be 39 patients available for this objective. A 95% exact binomial confidence interval on 5 responses out of 39 patients (expected if the addition of HCQ to IL-2 doubles the historic proportions of CR ~ 8%) would have width equal to 0.27 (0.07,0.34). For the secondary endpoints of OS and PFS, if patients are recruited over 15 months, observed for 15 additional months, and the true median survival is 16 months, then the expected width of the 95% confidence interval for median survival is 12.8 months.

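### Binary logistic models for complete response that carry the three-level prognostic class will probably have no finite class estimate, and the plan names no sparse-data method

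*Combined protocol and SAP*

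**What the plan says.** Section 13.2.4 sorts patients by number of risk factors (none, one or two, three or more; the same groups as section 6.1) and states: "This prognostic classification will be added to the baseline models described in Sections 13.2.1 to 13.2.3". Those models differ in kind. 13.2.1 plans a cumulative logit over ordered response levels, 13.2.2 a logistic and Cox comparison with historical high-dose IL-2, and 13.2.3 tabulation only.

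For the laboratory parameters, 13.2.5 continues: "Stepwise proportional hazards or logistic regression will be used to add variables to the models resulting from the analyses in Section 13.2.4". Section 13.2.6 does the same for changes in blood markers, adjusting for the 13.2.4 criteria. Neither section says whether response means CR or CR plus partial response, or how the class is coded. No penalised or exact method, collapsing rule or minimum count per class is given.

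On sample size, 13.4 says "there will be 39 patients available for this objective". Section 2.18 says "we are accruing another 21 patients to assess response in addition to the first five patients" at 600 mg/d, which makes 26 at that dose. The 13 patients treated at 1200 mg bring the total to 39.

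**The concern.** Maximum-likelihood logistic regression has no finite estimate for a categorical factor when a non-empty level has 0% or 100% responders. With 26 to 39 patients, about one in nine of them poor risk, and roughly 2 to 7 complete responders, that pattern is likely before any marker enters the model.

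Software may not make it obvious. The output can show a large negative coefficient, a huge standard error, a Wald p-value near 1 and the full sample size, and a reader could take this as evidence that the class does not matter. A marker effect labelled as adjusted for prognosis would also rest on fewer informative patients than the printed sample size suggests.

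**Working it through.** The plan states no figure for these models, so there is none to reproduce. The interval in 13.4 concerns the primary proportion and is not used here.

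**Inputs**
- Risk mix 19/70/11% good/intermediate/poor (section 2.2, the high-dose IL-2 Select trial). The documents give no mix expected for this trial, so this is an assumption.
- CR rate 8/95 = 8.4% (13.3.2), and doubled, 16.8% (the doubling hypothesis of 2.17 and 13.4).
- Any response: 22/95 = 23% (2.3) to 28% by investigator review (2.2).
- n = 39 or 26. Rates are equal across classes unless stated.

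**Formula.** For class sizes g₁, g₂, g₃ and rate p, P(no finite estimate) = 1 − Π[1 − (1−p)^gᵢ − p^gᵢ], taken over non-empty classes.

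**At the expected class sizes.** For n = 39 the classes are about 7/28/4.
- p = 0.084: P(no responder) is 0.540, 0.085 and 0.703. So 1 − 0.460 × 0.915 × 0.297 = 0.875.
- p = 0.168: P(no responder) is 0.275, 0.006 and 0.478. So 1 − 0.725 × 0.994 × 0.522 = 0.624.

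For n = 26 (about 5/18/3) the same steps give 0.935 and 0.756.

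**Averaged over random class sizes** (exact multinomial enumeration):

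| Endpoint and rate | n = 39 | n = 26 |
|---|---|---|
| CR 8.4% | 0.87 | 0.93 |
| CR 16.8% | 0.64 | 0.79 |
| Any response 23% | 0.49 | 0.68 |
| Any response 28% | 0.40 | 0.61 |

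**Sensitivity**
- Poor share from 5% to 15%: CR stays within 0.56-0.89 (n = 39) and 0.75-0.93 (n = 26). Any response at 25-28% with n = 39 runs from 0.60-0.63 down to 0.30-0.35.
- CR falling with risk (assumed 25/16/8%): 0.75 (n = 39) and 0.84 (n = 26).
- Entry requires Karnofsky status of at least 80%, so that risk factor is always absent. This can only make the poor class smaller than in a population without the restriction.

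**Information lost.** For CR, the average share of patients in a class that contributes nothing to the other coefficients is 10-23% (n = 39) or 16-34% (n = 26).

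**What a fit looks like.** Take responders 2/7, 8/28 and 0/4 plus a simulated marker, fitted by ordinary logistic regression in R. The poor-class coefficient is −16.6 with standard error 1978 and Wald p = 0.99. There is no warning, and n is reported as 39. In a parallel fit with another simulated marker, removing the four poor-risk patients left the marker coefficient (−0.583) and its standard error (0.512) unchanged.

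**What survives.** Take responders 0/5, 4/18 and 0/3. The log-likelihood is −9.535 with the class and −11.162 without it. The likelihood-ratio statistic is 2 × 1.628 = 3.26 on 2 df, p = 0.20.

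**Firth on the same data.** With the class alone, Firth's penalty adds 0.5 to each cell. Against intermediate (4.5/14.5), the odds ratios are (0.5/5.5)/(4.5/14.5) = 0.29 for good and (0.5/3.5)/(4.5/14.5) = 0.46 for poor. Profile intervals are 0.002-3.6 and 0.003-6.3.

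**Other planned models** (simulation)
- Cumulative logit: no finite estimate in 7-21% (n = 39) or 18-37% (n = 26), with an assumed progression share of 40-60%.
- Logistic model pooled with 95-123 historical patients, if patient-level classes exist: about 1-10% at rates of 16-25% and 30-39% at CR 8% (n = 39).
- Cox model for OS: a class without an event in about 5% (n = 39) or 13% (n = 26). Cox model for PFS: under 1%.

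**The case against.** The strongest reply is that 13.2.4 does not itself name a trial-only binary model for CR. It builds on a cumulative logit, a historical comparison and Cox models, all usually estimable. This is right, and it limits the point to the logistic models of 13.2.5 and 13.2.6 and to any binary response model fitted under 13.2.4.

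A reader might infer that objective 5 gets no answer. The documents do not support that. The objective concerns clinical outcome in general, the OS and PFS models nearly always work, and a likelihood-ratio test of the class survives separation.

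A reader might also infer that patients are dropped or that all standard errors are invalid. Neither is so: the loss is of information, and only the Wald inference for the separated class is meaningless. Nor need the software stop with an error; it commonly returns a fit.

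It also stands that the size depends on choices the plan leaves open. For any response at n = 39 the chance is below one half. If the class entered as an ordered 0/1/2 score, ordinary maximum likelihood would fail for CR in only 1-9% (n = 39) or 7-23% (n = 26). That score assumes a trend: in the 0/5, 4/18, 0/3 example it gives an odds ratio of 1.29 per step (0.21-8.7) and hides the non-monotone pattern.

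The remark in 13.2.2 that its comparisons are not powered is no answer, because it concerns precision and not whether an estimate exists.

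**Conclusion.** The point holds for binary logistic models of CR fitted to trial patients with the class as three categories. There a non-finite class estimate is the likely result: about 64-87% at n = 39 and 79-93% at n = 26. For any response it is 40-49% and 61-68%. These figures rest on the borrowed risk mix and on equal rates across classes; the sensitivity ranges move the size but leave CR above one half throughout. The consequence is unusable class estimates and Wald inference, plus some lost information for marker effects, in secondary and correlative analyses. The primary CR proportion, the monitoring rule and the survival analyses do not depend on it.

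**What to change.** In 13.2.4 to 13.2.6, state that any binary response model will be fitted by Firth penalised logistic regression, with profile penalised-likelihood intervals and tests replacing Wald ones, including at the stepwise entry steps. Report responders and patients per prognostic class beside each model. The rule works under either definition of response. Keep Cox regression for OS and PFS and the cumulative logit of 13.2.1. An ordered 0/1/2 score may be added as a sensitivity analysis, but the main model should not depend on its trend assumption.

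The cost is a few lines of SAP wording and a standard option in SAS or R, the software the plan names. The downside is slight shrinkage of the estimates. Intervals will still be wide, because no estimator makes up for so few responders.
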